8.3.3.2. Sensitivity Analysis of Primary Endpoint

Sensitivity analysis of the primary endpoint will be performed to assess the robustness of the primary analysis results in the presence of missing data. For participants who terminate from treatment prior to the end of the analysis period due to adverse event, noncompliance with study procedures, death, physician decision, or use of a prohibited medication, missing measurements will be considered missing not at random (MNAR); for all other participants having missing measurements, missing values will be considered missing completely at random (MCAR).

For FAS monotherapy subjects having missing TETRAS Performance Subscale Item 4 (upper limb tremor) total score data at any visit, and, separately, for FAS subjects overall, all missing data (MCAR or MNAR) will be imputed via multiple imputation (50-100 iterations, depending on system run time) using treatment based regression methodology which includes baseline TETRAS Performance Subscale Item 4 (upper limb tremor) total score in the model, with minimum and maximum possible integer values of 0 to 24, respectively (example SAS code is found in Appendix C). The MMRM model, including the selected covariance structure, used for the main analysis of the primary efficacy endpoint will be repeated for each imputation, and the results combined and reported. The covariance matrices resulting from the MMRM run on each imputation will be combined into an overall covariance matrix will be passed to the MCP-Mod analysis to perform sensitivity analysis of the dose-response relationship. SAS code associated with this sensitivity analysis is noted in Appendix C.

If the sensitivity analysis yields a result/conclusion that is different from the result of the primary analysis, the nature of the discrepancy will be examined in order to clearly explain the discrepancy based on statistical principles, and the discrepancy will be discussed in the clinical study report.

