8.3.3.1. Primary Analysis

The estimand for the primary efficacy endpoint is defined as follows:

- There are 4 treatment groups for the monotherapy participants to be evaluated: SAGE-324 (15 mg, 30 mg, 60 mg) and placebo.
- The target population consists of the monotherapy participants aged 18 to 80 years and have a diagnosis of ET with combined total upper limb TETRAS Performance Subscale Item 4 of at least 12 with the dominant upper limb score of at least 6 and baseline TETRAS ADL score of at least 20.
- The outcome for the primary efficacy endpoint is the change from baseline in TETRAS Performance Subscale Item 4 score on Day 91 in the monotherapy cohort.
- The population-level summary measure is the dose-response of different doses of SAGE-324 and placebo for the monotherapy cohort.
- The treatment/hypothetical policy strategy will be adopted for the primary endpoint. For data collected after the intercurrent events, such as rescue medication, the treatment policy strategy will be used. For data not available after the intercurrent events, like premature discontinuation of study treatment, the hypothetical policy strategy will be adopted. This means that the dose-responses of different dose groups will be analyzed using all observed on-study data, using appropriate visit mapping specified in Table 2, regardless of the occurrence of the intercurrent event, including use of additional medication, premature discontinuation of treatment for any reason, or other protocol violations.

The observed value, change from baseline, and percent change from baseline of the TETRAS Performance Subscale Item 4 (upper limb tremor) scores (individual and total score by side and combined) will be summarized descriptively by randomized treatment at each scheduled time point.

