The primary endpoint will be analyzed using a mixed effects model for repeated measures (MMRM); the model will include treatment, baseline TETRAS Performance Subscale Item 4 (upper limb tremor) total score, assessment timepoint, and timepoint-by-treatment as explanatory variables. All explanatory variables will be treated as fixed effects. All postbaseline clinic visits will be included in the model. An unstructured covariance structure will be used to model the within-participant errors. The Kenward-Roger approximation will be used to estimate denominator degrees of freedom. If there is a convergence issue with the unstructured covariance model, Toeplitz or Autoregressive (1) [AR(1)] covariance structure will be used, following this sequence until convergence is achieved. When the covariance structure is not unstructured, the sandwich estimator for the variance covariance matrix will be derived, using the EMPIRICAL option in the PROC MIXED statement in SAS. A pairwise comparison of change from baseline in TETRAS Performance Subscale Item 4

(upper limb tremor) for each SAGE-324 treatment group versus placebo will be provided. The p-values are not adjusted for multiplicity, so should be interpreted as nominal.

After the MMRM analysis by PROC MIXED, the estimated mean and covariance matrix at Day 91 will be passed to the MCP-Mod analysis (Bretz F, Pinheiro JC, Branson M, 2005) to test the dose-response relationship. A critical value will be determined from the joint multivariate normal distribution of the contrast test statistics at the overall one-sided alpha level of 0.05. If the test statistic exceeds this critical value, a nonflat dose-response relationship will be demonstrated.

In the analysis, multiple dose-response candidate models will be considered, including linear, loglinear, quadratic, exponential, logistic, Emax, sigEmax, and beta. In the trial design stage, these pre-specified candidate models based on available information were included in the MCP-Mod procedure. The parameters used to determine the contrast for testing assumes a change from baseline in TETRAS Item 4 upper limb total score in the placebo group of -1.2 points, a maximum decrease of -3.2 points from baseline for a dose response in the 15 to 60-mg dose groups. These can be done using the DoseFinding Package in R.

```
doses <-c(0, 15, 30, 60)
pboeff <- -1.2
acteff <- -2
quad <- guesst (d=45, p=1, 'quadratic')
exp <- guesst (d=45, p=0.5, 'exponential', Maxd=60)

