8.3.4. Analysis of Secondary Efficacy Variables

Summarization and analysis of the secondary efficacy variables will be performed for the monotherapy cohort (main analysis), adjunct therapy cohort (for directional investigation, excluding MCP-Mod analysis), and overall.

The primary, sensitivity, supportive, and subgroup analyses performed for the primary endpoint will be repeated for the secondary endpoint, change from baseline in TETRAS ADL composite score.

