APPENDIX C. SAS CODE FOR ANALYSIS OF PRIMARY EFFICACY ENDPOINT

Example code for MMRM:

The ODS statement is used to create output datasets, particularly COVB, for subsequent MCP Mod analysis.

```
Proc mixed data=[input dataset name]
	method=reml covtest alpha=0.05;
Where CHG ne .;
Class SUBJID TRTP(ref='Placebo') AVISITN;
Model CHG = BASE TRTP AVISITN TRTP*AVISITN /
	htype=3
	ddfm=KENWARDROGER
	residual solution covb;
Repeated AVISITN / sub=SUBJID type=[desired covariance structure];
Lsmeans AVISITN * TRTP / cov pdiff cl alpha=0.05;
ODS output
	solutionf=[output dataset name]
	covb=[output dataset name];
Run;
```

Example code for imputation of monotone missing data:

```
Proc mi data = [input dataset name]
        out = monotone(rename=(_imputation_=impn))
        nimpute=20
        seed=XXXXXX
        min = . . 0 0 0 0 0 0 0 0
        max = . . 24 24 24 24 24 24 24 24
        round = . . 1 1 1 1 1 1 1 1;
    Var trtpn base
        avisitn8 avisitn15 avisitn29 avisitn43
        avisitn57 avisitn71 avisitn91 avisitn97;
    MCMC impute=monotone chain=multiple;
    EM maxiter=500 converge=0.00001;
    Run;
```

Example code for treatment-based imputation of non-monotone missing data:

Monotone regression(/details);
Run;

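### The missing-data sensitivity analysis labels some dropouts MNAR but imputes every missing value the same way, so it never tests the MNAR mechanism it declares

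*SAP*

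**What the plan says.** SAP 8.3.3.2 gives the aim as "to assess the robustness of the primary analysis results in the presence of missing data". It then sorts missing scores by reason. After a treatment stop for an adverse event, poor compliance, death, a physician's decision or a prohibited drug, "missing measurements will be considered missing not at random (MNAR"; everyone else's are called MCAR. The next paragraph treats the two classes together: "all missing data (MCAR or MNAR) will be imputed via multiple imputation (50-100 iterations, depending on system run time) using treatment based regression methodology", with the baseline Item 4 total in the model. The primary MMRM is refitted to each completed data set and the combined result goes to MCP-Mod.

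Other relevant text:

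- SAP 8.3.4 extends the plan: "The primary, sensitivity, supportive, and subgroup analyses performed for the primary endpoint will be repeated for the secondary endpoint".
- SAP 8.3.3.1, on the estimand: "For data not available after the intercurrent events, like premature discontinuation of study treatment, the hypothetical policy strategy will be adopted". On the MMRM: "All postbaseline clinic visits will be included in the model", which takes in the Day 97 TETRAS.
- SAP Appendix C also puts Day 97 in the imputation ("avisitn57 avisitn71 avisitn91 avisitn97"). Its first step completes the data to a monotone pattern ("MCMC impute=monotone chain=multiple").
- Protocol 13.2 promises imputation-based sensitivity analyses and names no MNAR method.

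**The concern.** A sensitivity analysis is informative when it changes the assumption that cannot be checked. Here that assumption is how participants who stopped treatment would have scored at Day 91. The SAP itself says that for one class the missingness depends on the unseen values, then imputes that class as if it did not.

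Adverse events head the MNAR list, and such stops are plausible. Protocol 5.2 reports earlier events that led to dose reduction or discontinuation, and SAP 5.1 permits no dose reduction in this study.

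If the check agrees with the primary, as it almost must, that agreement is likely to be read as robustness. SAP 8.3.3.2 asks for discussion only if the two differ. A reader would not learn whether the conclusion survives a modestly worse course in the MNAR class. The same gap passes to the ADL composite.

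**Working it through.** **1. The plan's own figure.** Inputs from SAP 5.2: placebo change -1.2, maximum change -3.2 (difference -2.0), SD 2.5, 22 evaluable per arm, one-sided alpha 0.05, stated power 80%. The eight candidate shapes were rebuilt from the inputs in SAP 8.3.3.1, with the linlog offset assumed to be 0.01 x the maximum dose. Power averages 82.0% over the shapes (65% for beta to 86% for Emax). 22/(1 - 0.15) = 25.9, so 26 per arm. The stated figures are reproduced closely enough to use the same set-up below.

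**2. Where the label goes.**

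- The 8.3.3.2 text defines two classes and then applies one imputation to both.
- The legible Appendix C code uses treatment, baseline and visit scores. It splits by missingness pattern, not by reason for stopping. It shows no delta, reference arm or MNAR statement.
- The Per Protocol repeat (SAP 8.3.3.3) changes the analysis set, not the missing-data assumption.
- Appendix D lists one imputation table per endpoint (14.2.1.3 and 14.2.2.3).

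**3. Who is affected.** Under Protocol 8.4.1, participants who stop early are encouraged to attend an EOT visit and visits 7 and 14 days later. SAP 8.3.2 maps the later ones by days since last dose to Day 97 or Day 104. Such a participant will usually have no Day 91 score, unless a visit falls in the Day 82-96 window or a nominal Day 91 visit is attended. An off-drug Day 97 score, where there is one, enters both the MMRM and the imputation, so it does not separate the two analyses.

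**4. How closely the two analyses agree.** Set-up: 400 simulated trials per setting, 26 per arm, 8 post-baseline visits. In each arm 4 stop at random and lack every later visit through Day 91, but have Day 97 observed. Arm is a class variable, 50 imputations, baseline omitted. The settings cross linear and Emax effects with compound-symmetry 0.7 and AR(1) 0.9 correlation.

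- Mean 60 mg differences were the same for MMRM and MI: -2.05, -1.99, -1.92 and -1.99.
- The largest gap in any trial was 0.09 points, and the MCP-Mod verdict matched in 99.0-99.8% of trials.
- With Day 97 missing as well (linear, compound symmetry), the means were -2.00 and -2.01, the largest gap 0.08 and the match 99.8%.

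**5. What using the label would show.** If k of 26 in an active arm are in the MNAR class and their imputed scores are worsened by delta, the arm's difference from placebo moves by (k/26) x delta:

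- k = 2, 4, 8 gives 0.08, 0.15, 0.31 x delta.
- Full loss of the assumed -2.0 at 60 mg (delta = 2) gives -2.0 + 2k/26 = -1.85, -1.69, -1.38.

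**6. Tipping delta for MCP-Mod.** Assumptions: 26 per arm, 4 imputed in each, optimal contrasts, multivariate-normal critical value 1.993. Active means shift by p x delta, with p = 4/26 (all imputed participants in the class) or 2/26 (half).

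Variance of an arm mean = [6.25 + average over arms of p(1-p) x delta²]/26 + 6.25 x (1/22 - 1/26), with p = 0 for placebo. At delta = 0 this is 6.25/22 = 0.284, SE 0.533.

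Worked case: linear effects at 75% of plan, p = 4/26.

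- The planned linear differences 0, 0.5, 1.0, 2.0 have mean 0.875 and centred sum of squares 2.1875. The contrast value is 0.75 x √2.1875 = 1.109, and the statistic is 1.109/0.533 = 2.08.
- At delta = 0.5 each active mean loses 0.077. The linear coefficients of the active arms sum to 0.592, so the contrast loses 0.046.
- The variance becomes 0.285 and the statistic (1.109 - 0.046)/0.534 = 1.99, which is the critical value.

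| 60 mg difference | Linear: largest statistic | Tipping delta, 4/26 | 2/26 | Emax: largest statistic | Tipping delta, 4/26 | 2/26 |
|---|---|---|---|---|---|---|
| -2.0 | 2.77 | 3.94 | 6.45 | 2.95 | 3.37 | 5.93 |
| -1.8 | 2.50 | 2.60 | 4.40 | 2.65 | 2.42 | 4.36 |
| -1.6 | 2.22 | 1.22 | 2.25 | 2.36 | 1.40 | 2.61 |
| -1.5 | 2.08 | 0.50 | 0.96 | 2.21 | 0.86 | 1.63 |

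A repeat of this calculation matched every tipping value to 0.01.

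**The case against.** - **MAR suits the estimand.** For data unavailable after an intercurrent event the SAP adopts a hypothetical strategy, and MAR imputation is a reasonable way to estimate it. This stands. It defends the primary estimate, but it does not make a second MAR analysis a test of data the SAP calls MNAR.
- **The code is incomplete.** The second PROC MI block in Appendix C is legible only in its last lines, so an MNAR statement there cannot be excluded. This stands as a limit. The reading rests on the 8.3.3.2 text, which handles both classes together and describes no shift.
- **The simulation is not the visible code.** The legible block has no CLASS statement, so arm appears to enter as a number, and it rounds to integers. A smaller rerun with both features (40 trials per setting, 20 imputations) gave a gap of up to 0.29 points at 15 mg. Gaps at 60 mg stayed at 0.10 or less, and mean gaps were 0.02-0.09. The exact agreement rates in step 4 therefore do not describe that code, but near-agreement survives.
- **The sizes are assumed.** The 15% in SAP 5.2 is a nonevaluable rate, not a Day 91 missing rate within the Full Analysis Set. The class split and deltas are not in the documents, nor is the share of stoppers who attend Day 97. Any near-threshold result tips easily, and at planned effects tipping needs more than full loss of the 2.0-point effect. All true, but the planned check cannot show which case applies.
- **Relabelling would do.** Dropping the MNAR label, or calling the analysis a MAR check, would remove the contradiction. It would not supply the robustness answer the section sets out to give.

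**Conclusion.** The concern holds. In the legible plan the MNAR class is defined and never used, and no other planned analysis tests it. Agreement with the primary would not support a claim of robustness to that mechanism, for either the primary or the secondary endpoint.

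The fault lies in the sensitivity analysis only. No bias in the primary estimate is claimed, and the primary test, alpha and sample size are unaffected. It should be fixed, but it does not invalidate the design.

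The practical size depends on the strength of the result. With 4 of 26 missing per arm and all in the MNAR class, a result as strong as planned needs a shift of about 3.4-3.9 points to tip, while one at 75% of the assumed effects needs 0.5-0.9. With half in the class the figures are 5.9-6.5 and 1.0-1.6. These are illustrations under assumed missingness, not predictions for this trial.

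**What to change.** Before unblinding, prespecify one delta-adjusted tipping-point analysis for MNAR-class participants in the SAGE-324 arms:

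1. Impute all missing data under MAR, as planned.
2. Add delta (0, 0.5, 1.0 and so on) to every imputed post-discontinuation Item 4 total in that class. Include Day 91 values that the MCMC step fills because Day 97 is observed. A data step after imputation does this, as does FCS with an MNAR adjustment. An MNAR statement in the monotone step alone would miss those values. Leave observed scores unshifted.
3. Refit the MMRM. Pass the pooled Day 91 means and Rubin's total covariance, average W + (1 + 1/m)B, to MCP-Mod. Report the delta at which the largest statistic falls below its critical value, beside each arm's estimated effect, because one common delta can exceed full loss at the lower doses.
4. Keep the other class under MAR with delta 0.
5. Optionally add a reference-based analysis, labelled as addressing a different target.
6. Repeat for the ADL composite with its own delta grid.

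In the same edit, reconcile `nimpute=20` in Appendix C with the 50-100 in the text, and remove integer rounding of a total that moves in 0.5-point steps (SAP 8.3.1.1).

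Cost: SAP wording, a data step and a little more analysis, with no new data. The planned estimand is kept. The downside is that the sensitivity result may look less favourable.

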8.3.3.3. Supportive Analysis of Primary Endpoint

Summarization and analysis of the primary endpoint will be repeated based on the Per Protocol Set as a supportive analysis.

8.3.3.4. Subgroup Analyses of Primary Endpoint

The descriptive summarization and MMRM analysis of the primary endpoint will also be presented by the following subgroups:

• Age group: <65 years, 65 to 80 years

Statistical Analysis Plan Methods Version 1.0 17-Jun-2024 Protocol Number: 324-ETD-202 (Version 6.0 2 November 2023)

- Sex: Male, Female
- Race: White, Black or African American, Asian, Other
- BMI: $<18.5 \text{ kg/m}^2$, 18.5 to $<25 \text{ kg/m}^2$, 25 to $<30 \text{ kg/m}^2$, $\ge 30 \text{ kg/m}^2$
- Age at ET diagnoses: <40 years, 40 to 60 years, >60 years
- Age participant thinks ET started: <20 years, 20 to <40 years, 40 to 60 years, >60 years
- Years with ET diagnosis: <6 years, 6 to 10 years, and >10 years
- Years since participant thinks ET started: <6 years, 6 to 10 years, and >10 years
- Alcohol helps tremor: Yes (Intermediate, Worked Well), No (No, a little), NA
- Baseline TETRAS performance subscale part 4 upper limb tremor score on the dominant side: <7.5 and >7.5
- Baseline TETRAS performance subscale part 4 upper limb tremor score on the dominant side: < median and ≥ median
- Past treatment for ET (Yes, No)
- Response to past treatment for ET: Yes (Intermediate, Worked Well), No (No, a little), NA

If any of the subcategories has <5 patients fall into that category, the category will be combined with the next adjacent category with smaller counts. For example, if the number of patients falling into BMI category <18.5 kg/m² is <5, this category will be combined with the 18.5 to <25 kg/m² group. In the case of a variable of interest having only 2 subcategories and one of those subcategories has <5 patients, the variable will not be part of the sub-group analysis.

Forest plots for subgroup analysis for the primary endpoint at Day 91 – LS mean differences and associated confidence intervals – will be provided.

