8. SELECTION AND WITHDRAWAL OF PARTICIPANTS

8.1. Participant Inclusion Criteria

Participants must meet all of the following criteria to qualify for participation in this study:

- 1. Participant has signed an informed consent form (ICF) before any study-specific procedures or washout of drugs is started.
- 2. Participant is ambulatory and is 18 to 80 years of age, inclusive, at the time informed consent is obtained.
- 3. Participant is in good physical health and has no clinically significant findings (excluding ET), as determined by the investigator, on physical examination, including neurologic and mental status examinations, 12-lead ECG, or clinical laboratory tests.
- 4. Participant has a diagnosis of ET, as defined by all of the following criteria:
 - a. Isolated tremor syndrome consisting of bilateral upper limb action tremor
 - b. At least 3 years duration
 - c. With or without tremor in other locations (eg, head, voice, or lower limbs).
- 5. Absence of other neurological signs, such as dystonia, ataxia, or parkinsonism, isolated focal tremors (eg, voice, head), task- and position-specific tremors, sudden tremor onset or evidence of stepwise deterioration of tremor.
- 6. Participant has the following:
 - a. Scores at least 12 in the combined TETRAS Performance Subscale Item 4 (upper limb tremor) at both Screening and predose on Day 1
 - b. Scores at least 6 in the total TETRAS Performance Subscale Item 4 score for the dominant upper limb (the sum of the three items for either the right or left upper limb, whichever is dominant) at both Screening and predose on Day 1.
- 7. Participant has a baseline TETRAS ADL Subscale score of at least 20 at Screening.
- 8. Participant is willing to discontinue medications taken for the treatment of ET except propranolol at least 14 days or 5 half-lives (whichever is longer) prior to receiving IP. Medications taken for the treatment of ET that were discontinued prior to receiving IP may be resumed following Day 97. Participants in the adjunct therapy cohort must be on a stable dose of propranolol (maximum total daily propranolol dose up to 320 mg allowed) for the treatment of ET from 3 months prior to Screening through Day 97 of the study.
- 9. Participant is willing to limit use of alcohol to 2 units per day for males and 1 unit per day for females starting at least 1 week prior to Day 1 and through Day 97 of the study.

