8.3.1.1. Primary Efficacy Assessment

For the TETRAS Performance Subscale Item 4 (upper limb), three maneuvers/assessments will be completed for both arms, first for the right arm and then for the left, specifically Item 4a, limbs extended forward maneuver (postural tremor), Item 4b, wing-beating [elbows flexed] maneuver (postural tremor), and Item 4c finger-nose-finger maneuver (kinetic tremor). Each assessment is rated on a 0 to 4 scale of severity in 0.5-point increments, with higher scores indicating more severe tremor. The Performance Subscale Item 4 (upper limb) total score range for a given side (left or right) is 0 to 12, and for both sides combined is 0 to 24; if any component of a total score for a side or both sides is missing, the total score is not computed. Assessment of the TETRAS Performance Subscale Item 4 (upper limb) occurs at Screening and Days 1, 8, 15, 29, 43, 57, 71, 91/EOT, and 97.

The primary efficacy endpoint is the change from baseline in TETRAS Performance Subscale Item 4 (upper limb) total score at Day 91 in the monotherapy cohort for the Full Analysis Set.

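### As printed, the 7.5-point baseline-severity subgroup in SAP 8.3.3.4 assigns a dominant-side score of exactly 7.5 to neither category

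*SAP*

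**What the plan says.** SAP section 8.3.3.4 repeats the descriptive summary and the MMRM of the primary endpoint in a list of subgroups, with a Day 91 forest plot. One entry reads "Baseline TETRAS performance subscale part 4 upper limb tremor score on the dominant side: <7.5 and >7.5". The next entry splits the same variable "on the dominant side: < median and ≥ median".

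On the score itself, SAP section 8.3.1.1 says "Each assessment is rated on a 0 to 4 scale of severity in 0.5-point increments", and gives the "total score range for a given side (left or right) is 0 to 12, and for both sides combined is 0 to 24". Protocol section 8.1, inclusion criterion 6b, requires "Scores at least 6 in the total TETRAS Performance Subscale Item 4 score for the dominant upper limb", defined there as "the sum of the three items for either the right or left upper limb, whichever is dominant", at both Screening and predose on Day 1.

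The only general rule on category membership in section 8.3.3.4 concerns sparse categories: "If any of the subcategories has <5 patients fall into that category, the category will be combined with the next adjacent category with smaller counts". Section 8.3.4 repeats the subgroup analyses for the ADL composite.

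**The concern.** A prespecified two-way subgroup should put every eligible participant in exactly one category. With a strict sign on both sides, a participant at the cut point has no category. A programmer following the text would leave these participants out of this subgroup's summary, model and forest-plot rows, and the two categories would not add up to the Full Analysis Set. A programmer who noticed the gap would have to choose a side without a prespecified rule. The first outcome costs some precision. The second leaves a discretionary choice that the plan should have settled while the study was blinded.

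The stake is limited to one exploratory subgroup of the primary endpoint and its repeat for the secondary endpoint.

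**Working it through.** **Inputs.** Three maneuvers per side, each scored 0, 0.5, ..., 4 (SAP 8.3.1.1). Dominant-limb score = sum of the three, at least 6 at entry (Protocol 8.1). Cut: below 7.5 and above 7.5, both strict (SAP 8.3.3.4). Planned size: at least 104 monotherapy participants, 160 in total (SAP 5.2).

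**Step 1: reproduce the plan's score range.** Each maneuver has 9 possible values, so there are 9 × 9 × 9 = 729 combinations per side. The smallest sum is 0 and the largest is 3 × 4 = 12, in steps of 0.5. Both sides together reach 2 × 12 = 24. This matches SAP 8.3.1.1.

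**Step 2: is 7.5 attainable and eligible?** Yes. For example, 2.5 + 2.5 + 2.5 = 7.5. Of the 729 combinations, 52 sum to 7.5. Eligible totals run from 6.0 to 12.0, which is (12 − 6)/0.5 + 1 = 13 values; 7.5 is the fourth.

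**Step 3: apply the printed cut to the 13 eligible values.**

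| Category | Scores | Number of values |
|---|---|---|
| Below 7.5 | 6.0, 6.5, 7.0 | 3 |
| Above 7.5 | 8.0 to 12.0 | 9 |
| Neither | 7.5 | 1 |

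The printed rule classifies 12 of 13 values. With either side made inclusive, all 13 fall in exactly one category.

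**Step 4: does another rule place 7.5?** The sparse-category rule merges whole categories that have fewer than 5 patients; it does not assign a boundary value. No other text in the SAP does so.

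**Step 5: how many participants?** The documents give no baseline distribution, so this step is an assumption. Take a normal with mean m and SD s, rounded to half points and truncated to 6 to 12:

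share at 7.5 = [Φ((7.75 − m)/s) − Φ((7.25 − m)/s)] / [Φ((12.25 − m)/s) − Φ((5.75 − m)/s)]

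| m | s | Numerator / denominator | Share | Of 104 | Of 160 |
|---|---|---|---|---|---|
| 6.5 | 1 | 0.1210 / 0.7734 | 15.6% | 16.3 | 25.0 |
| 7.5 | 1 | 0.1974 / 0.9599 | 20.6% | 21.4 | 32.9 |
| 7.5 | 2 | 0.0995 / 0.8004 | 12.4% | 12.9 | 19.9 |
| 8.5 | 2 | 0.0878 / 0.8850 | 9.9% | 10.3 | 15.9 |
| 9 | 1 | 0.0656 / 0.9988 | 6.6% | 6.8 | 10.5 |
| 10 | 2 | 0.0457 / 0.8529 | 5.4% | 5.6 | 8.6 |
| 10 | 1 | 0.0092 / 0.9878 | 0.9% | 1.0 | 1.5 |

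Over means 6.5 to 10 and SDs 1 to 2, the share runs from about 1% to 21%: about 1 to 21 of 104 monotherapy participants. Within that grid the assumed mean matters most.

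**The case against.** The strongest objection is that the sign may be an artefact of reading the PDF. SAP section 8.4 contains a close parallel. In Table 6 (ECG windows) the Day 104 row prints a tolerance of +3 days and a window strictly after Day 97. In Table 7 (laboratory windows) the same row prints ±3 days and ≥ Day 97. The schedule of assessments gives ±3 for that visit, and the preceding Table 6 window ends at Day 96, so the inclusive sign is the one that leaves no gap. Loss of the lower bar from such symbols would explain both that row and the cut at 7.5.

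This stands as a serious possibility, but it is not shown. Within section 8.3.3.4 the inclusive sign survives in the adjacent entry ("< median and ≥ median") and in the BMI entry (≥30). In Table 6 itself, ± survives in the Day 29 row and ≤ in the Day 1 row. A typing slip in the SAP explains the text equally well, and only the source document can settle it.

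Two further objections stand in full. First, the SAP never says that participants at 7.5 will be excluded; it defines no category for them. Second, the median split on the same variable is a complete partition, so these participants are still analysed by baseline severity elsewhere in the same list.

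**Conclusion.** On the text as printed, the point holds in a limited form: a score of exactly 7.5 is attainable and eligible, and it is in neither category of this subgroup or of its repeat for the ADL composite. That part rests on enumeration alone. The size, about 1% to 21% of participants, rests wholly on the assumed truncated normal and should be read as a range of possibilities.

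A reader might infer more than this. One inference is that at least a tenth of the cohort is lost because 7.5 sits where baseline scores are densest. The documents do not support it: no baseline distribution is given, protocol section 5.1 describes moderate to severe disease, and with a mean of 9 or 10 the share falls below 10%. Another is that the efficacy conclusion is at risk. It is not: the primary MMRM in SAP section 8.3.3.1 uses the baseline Item 4 total score directly, without this cut, and the MCP-Mod step takes its inputs from that model. This is a minor point, and it is conditional on the sign in the source document.

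**What to change.** First check the sign in the source SAP. If it already reads ≥7.5, nothing needs to change. If it is strict there, define the categories in section 8.3.3.4 as <7.5 and ≥7.5, which matches the direction used for the median split. The change carries over to the ADL composite through section 8.3.4. Make it before unblinding, so that the placement of these participants is not chosen with treatment known. If the database has already been locked, SAP section 2 requires the change to be documented and discussed in the clinical study report.

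The cost is one character in the SAP and the matching condition in the subgroup programs. Sample size, data collection and the primary analysis are not touched.
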